### 10.3.1 Summary of baseline data and flow of patients

[figure not shown]
Randomization	Sample size calculation with the G* Power 3 program N=140	Randomization list generated in MS Excel at the commencement of the study by the Chief investigator: independent of assessment and intervention	Execution- randomization list will be held by the PI (ophthalmologist at REI) so that they know who is allocated into either the intervention or control groups according to the list.
Outcome measures		Trial description	Outcome recorded
Primary outcomes Dynamic stability	1.Eye gazing characteristics	Gazing duration on obstacles during the obstacle negotiation.  Area of interest and corresponding glazing duration during stair walking	
 
Gazing duration and frequency on obstacles and area of interest.
 
Heat map on area of interest from eye tacking device
 
 
all data will be recorded and saved in file name in the format: participant number-obstacle-trial1/2/3-date.

	2.Movement biomechanics	
-participants perform Timed up and go (TU&G) test involving getting up from chair ,then walking over 3m level ground, turning and walking back to sit down on the chair
 
- participants walk over a 3m level ground with obstacles of different contrast colour to background.
 
- accelerometers of head tilting and change in movement of centre of gravity will be recorded during TU&G test and during crossing over obstacles.
	
 
accelerometers data of change in head tilting and centre of gravity will be recorded
 
Duration in seconds of TU&G test
 
 
all data will be recorded and saved in file name in the format: participant number-obstacle-trial1/2/3-date.

Secondary outcomes	1.Refraction and visual acuity	-standardized protocol for routine visual function test	-vision 20/20, sphere cylinder, axis -DVA, NVA -IOL rotation (for Toric IOL group only)
	2.Questionnaire	Short Fall Efficacy Scale International Fear of Falling Questionnaire CAT-PROM 5 Quality of life Questionnaire	

- A CRF form has been prepared for this study

Vision and balance changes after bilateral implantation of Toric IOLs  
IRAS ID: 286913

**Modified CONSORT flow diagram  
for**

**Vision and balance changes using after bilateral  
implantation of Toric versus non-Toric intraocular lenses in  
Cataract patients with astigmatism**

Cite as: Boutron I, Altman DG, Moher D, Schulz KF, Ravaud P. CONSORT Statement for Randomized Trials of Nonpharmacologic Treatments: A 2017 Update and a CONSORT Extension for Nonpharmacologic Trial Abstracts. *Annals of Internal Medicine*. 2017 Jul 4;167(1):40–7.

Vision and balance changes after bilateral implantation of Toric IOLs  
 IRAS ID: 286913

### 10.3.2 Primary outcome analysis- Dynamic stability in three functional activities

The following outcomes will be collected at three time points: before surgery, 3 to 6 months after first and second eye surgery.

Outcome measures	Data collected	Data type/ details	Quantitative Statistical Analysis
Dynamic stability during turning, obstacle crossing and stair walking	Accelerometers data (angular position and acceleration) of change in head tilting and centre of mass will be recorded  Performance of TU&G test	Interval  Centre of mass and head movement will be calculated using ProMove 3D (Inertia Technology, The Netherlands) and MATLAB.  The angular position, velocity and acceleration of the sensors will be tracked on each participant  Duration in seconds of TU&G test	The average reading of the 3 trials in each functional activity will be calculated.  Mixed ANOVA and post-hoc Bonferroni tests will be used to determine the differences between the Toric IOLs group and Monofocal IOLs group before surgery and 6 months after second eye surgery.

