### 3. OBJECTIVES AND OUTCOME MEASURES/ENDPOINTS

#### 3.1 Primary objective

The objective of the study is to compare the effects of Toric intraocular lens versus Monofocal intraocular lens replacement on dynamic stability among cataract patients with astigmatism using a randomised controlled trial.

It is hypothesized that Toric intraocular lens will have additional correction of astigmatism after the cataract surgery resulting in and better outcomes in dynamic stability and higher chance of “spectacle-free”.

There are two arms of the trial: Monofocal Toric intraocular lens versus Monofocal non-Toric intraocular lens

The research question is based on the PICOT criteria:

P Population	Cataract patient with astigmatism >1.0DD awaiting intraocular lens replacement surgery
I Intervention	Monofocal Toric intraocular lens
C Comparison group	Monofocal non-Toric intraocular lens
O Outcome of interest	Primary- Dynamic stability will be measured by motion sensor during functional movements (crossing obstacles, turning and stair walking)  Secondary- Eye tracking characteristics, visual function, risk of fall, vision specific quality of life questionnaire and Toric IOL rotation.
T Time	Before operation (T1) and 3-6 months after each eye operation (T2, T3)

Vision and balance changes after bilateral implantation of Toric IOLs  
IRAS ID: 286913

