## 7.7 Trial assessments

Three study visits will be arranged for each participant who have given written informed consent to take part in the study.

**Study visit 1:** Pre-surgery baseline assessment will take place at the PAHC building of UoP, at least one week before the cataract surgery. After the participants have the cataract screening appointment at REI, they usually wait 3 to 6 weeks before the cataract surgery. The first study visit for the pre-operation baseline assessment will be arranged during this period. This also gives participants extra time to reconsider taking part in the study from when they signed the informed consent form at the REI. The study coordinator will reconfirm informed consent over the phone or by email (whichever is the preferred contact method) with the participant before arranging the first study visit and at the start of each study visit. If a participant needs to delay or cancel the cataract surgery due to a medical reason, the study coordinator will liaise with the PI who is the Ophthalmologist to confirm the participant is still suitable to take part in the study.

Intervention: participants will be randomized into two groups. One group will receive Toric Monofocal IOLs and the other group will receive standard non-Toric Monofocal IOLs.

**Study visit 2:** Reassessment of outcome measures will take place three to six months after first eye surgery at the PAHC building of UoP.

**Study visit 3:** Reassessment of outcome measures will take place three to six months after second eye surgery at the PAHC building of UoP.

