## **10. STATISTICS AND DATA ANALYSIS**

### **10.1 Sample size calculation**

Sample size test calculation was carried out with the G\*Power 3.1 program (Faul *et al.*, 2007) for comparison of the main outcome measure of dynamic balance (between IOL design) using mixed ANOVA (repeated measures, between factor being the type of IOL).

Based on of the dynamic balance measurement (JERK score) in a previous study (Mancini *et al.*, 2011) an estimated medium effect size (0.25) will be used. With a power of 85% and level of significance ( $p$ ) set at 0.05 and effect size of 0.25, 55 participants will be required in each group (Monofocal vs Toric IOL). Accounting for a 20% drop out rate, 70 participants will therefore be recruited in each group (A total of 140 participants).

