### **10.3 Statistical analysis plan**

All data will be assessed for normality using a combination of assessing histogram plots and the Shapiro-Wilks Normality Test. Descriptive summary statistics for outcome measures relating to vision (acuity and refraction) will be recorded as mean +/- standard deviation.

Mixed ANOVA and post-hoc Bonferroni tests will be used to determine the statistical differences in the baseline characteristics and outcome measures between the Toric monofocal IOLs group and the non-Toric monofocal IOLs group. The between-subjects factor would be type of IOL lens and the within-subjects factor would be time (pre-surgery vs post-surgery). Level of significance will be set at 0.05.

Vision and balance changes after bilateral implantation of Toric IOLs  
IRAS ID: 286913

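### The primary comparison uses two of three visits, so visit 2 has no stated between-arm contrast and anyone without visit 3 contributes nothing

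*Combined protocol and SAP*

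**What the plan says.** Three assessments are planned. The research question in 3.1 gives them as "Before operation (T1) and 3-6 months after each eye operation (T2, T3", and 3.6, 7.7, the opening line of 10.3.2 and the schedule in Appendix 2 agree. The movement, gaze, vision and questionnaire assessments are scheduled at all three.

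The analysis text is narrower. Section 10.3 plans a mixed ANOVA in which "the within-subjects factor would be time (pre-surgery vs post-surgery". Section 10.3.2 applies it to "differences between the Toric IOLs group and Monofocal IOLs group before surgery and 6 months after second eye surgery", and 10.3.3 uses the same pair for gaze, refraction and acuity, and questionnaires. No section gives visit 2 a between-arm contrast.

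The final visit is dated in two ways. Section 7.7 says "Reassessment of outcome measures will take place three to six months after second eye surgery", while the analysis cells say 6 months. The patient-involvement summary records a move from after 6 months to 3 to 6 months, so the cells may simply not have been updated.

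On incomplete follow-up, 10.6 withdraws participants who miss a visit and do not respond, and discards their data. Section 7.2 says data gathered before withdrawal will be analysed. No imputation or likelihood-based method is described.

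**The concern.** A mixed ANOVA with two time levels needs both values from each participant. Someone assessed at visits 1 and 2 but not at visit 3 has no post-surgery value and leaves the comparison, even though an intermediate measurement is in hand. If that measurement predicts both who is lost and how they would have done, setting it aside can bias the arm difference.

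Two further things are at stake. The T2 part of the research question has no planned answer. The primary endpoint is also tied to a time at which no visit is fixed, so it is unclear whether a visit 3 held at three or four months counts.

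**Working it through.** **1. Which visits the plan's own figure uses.** Section 10.1 sizes the trial "using mixed ANOVA (repeated measures, between factor being the type of IOL", and "an estimated medium effect size (0.25) will be used", with 85% power and alpha 0.05. It gives neither the number of measurements m nor their correlation ρ. For the between-group test,

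λ = f² × N × m / (1 + (m − 1)ρ), with 1 and N − 2 degrees of freedom.

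- m = 2, ρ = 0.5: λ = 0.0625 × 110 × 2 / 1.5 = 9.17, power 0.851. This reproduces N = 110 exactly.
- m = 3, ρ = 0.5: N = 98, where λ = 0.0625 × 98 × 3 / 2 = 9.19, power 0.851.
- m = 3 gives λ = 9.17 at N = 110 only if 1 + 2ρ = 0.0625 × 110 × 3 / 9.17 = 2.25, so ρ is about 0.62.

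The figure fits a two-measurement design but does not prove one.

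**2. What the planned contrast is.** With two time levels, the arm-by-time test is a comparison of mean change (visit 3 minus visit 1) among participants with both values.

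**3. Bias.** The inputs are 70 per arm and 20% loss (10.1), plus assumptions that the documents do not supply: a true effect of -0.50 SD; correlations of 0.5 (baseline with each later visit) and 0.7 (visit 2 with visit 3); and everyone lost having attended visit 2. Suppose completers in one arm have a visit-2 mean shifted by s from that arm's full mean. Their visit-3 mean then shifts by 0.7s and their baseline mean by 0.5s, so

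bias of the change contrast = (0.7 − 0.5) × s = 0.2s.

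Simulation with 3000 replicates, control-arm loss logistic in visit 2 (log-odds slopes 1 and 2):

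| Loss of visit 3 | Planned change contrast | Three-visit model |
|---|---|---|
| Random | unbiased | -0.50 |
| Follows visit 2, control arm only | -0.46 to -0.45 | -0.50 |
| Follows visit 2 equally in both arms | -0.50 to -0.51 | -0.50 to -0.51 |

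The shortfall is (0.50 − 0.46)/0.50 = 8% to (0.50 − 0.45)/0.50 = 10%, or 11% before rounding. It corresponds to s = 0.04/0.2 = 0.20 to 0.05/0.2 = 0.25 SD. When s is the same in both arms, it cancels.

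**4. Precision, 56 completers per arm.**

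- Change score: √(2 × 2(1 − 0.5)/56) = √(2/56) = 0.189.
- Baseline-adjusted completers: √(2 × (1 − 0.5²)/56) = √(1.5/56) = 0.164.
- Three-visit model (simulated, random loss): 0.158.

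The variance falls from 0.0357 to 0.0268 to 0.0250. Of the total fall of 0.0107, 0.0089 (83%) comes from using baseline as an adjustment. Visit 2's own share is 1 − (0.158/0.163)² = 6%, from the simulated standard errors of 0.163 and 0.158. With one common correlation of 0.3 to 0.7, and 7 to 14 per arm lost after visit 2, the completers' variance is only 0.6 to 3.5% larger than the three-visit model's.

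**The case against.** The best defence has four parts.

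- **The trial concerns bilateral implantation.** Making the final, two-eye visit primary is reasonable. This stands, and the fix keeps it.
- **Bias needs loss that differs by arm, and nothing in the documents points to it.** Participants stay masked until their final visit (7.4), and 13.3 reports few dropouts in earlier lens trials. This also stands. The bias is conditional, and a three-visit model guards against it without showing that it will occur.
- **The two-level wording is loose.** Post-surgery in 10.3 does not by itself exclude visit 2. But 10.3.2 and 10.3.3 name only the time after second-eye surgery, so the gap remains.
- **Visit 2 is not a clean first-eye measurement.** It falls 3 to 6 months after first-eye surgery, while 8.6 puts second-eye surgery at around four months. Some visit-2 assessments may follow the second operation. This stands, and it is a reason to state the visit-2 analysis in advance.

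Two stronger readings are tempting. A reader might infer a bias of about 22%, because a baseline-adjusted completers analysis gives -0.39 under one-arm loss. That is not the analysis planned; the planned change contrast loses about half as much. A reader might also infer that visit-2 data feed no planned result. Section 10.3.3 has post-operative analyses not restricted to visit 3 (the additional acuity ANOVA, the astigmatism vectors, lens tilt, decentration and rotation), and so does the rotation subgroup in 10.4. What the documents support is that visit 2 is assigned to no between-arm contrast.

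**Conclusion.** The point holds. The primary analysis and the matching secondary cells use two of three scheduled visits, and they date the second at a time that conflicts with the visit window.

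The likely numerical harm is modest. The estimate is 8 to 11% too small if loss tracks visit 2 in one arm only, which is 0.04 to 0.05 SD against a standard error of about 0.19. There is no bias if loss is random or shifts both arms equally. These figures rest on the assumed correlations, effect and loss pattern in the working. By the formula there, the bias shrinks as the visit 2 to visit 3 correlation approaches the baseline to visit 2 correlation.

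The case for change rests on the unanswered T2 question, the undefined endpoint time and a weaker missing-data assumption. The precision gain is real, but it comes mostly from baseline adjustment; visit 2 adds only a few percent in variance.

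**What to change.** - **Model.** In 10.3, 10.3.2 and 10.3.3, for continuous outcomes, replace the two-level mixed ANOVA with a likelihood-based repeated-measures model. Use visit (1, 2, 3) as categories, arm by visit, baseline means constrained equal (or baseline as a covariate), and all randomised participants with any measurement.
- **Primary contrast.** Make it the arm difference at visit 3, described by its window of 3 to 6 months after second-eye surgery, so that the analysis text and 7.7 agree.
- **Secondary contrast.** Make it the arm difference at visit 2. State in advance how visit-2 assessments made after second-eye surgery are analysed, for example by recording surgery status at each visit 2 and repeating the contrast without those assessments.
- **Missing data.** Replace the discard rule in 10.6 with the rule in 7.2 that data collected up to withdrawal are used. Without this, the model could not include everyone randomised.

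The cost is analysis-plan wording and slightly more analysis work. No new visits or data are needed.

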### 10.3.3 Secondary outcome analysis

Outcomes	Data collected	Data type	Quantitative statistical Analysis
Eye glazing characteristics during obstacle crossing and stair walking	Gazing duration on obstacles and area of interest on environment during stair walking  Area of interest determined by heat map (area with highest frequency of gazing)	Interval  Gaze pattern of location of hotspots and duration of gaze will be collected using Tobii pro eye tracker.  % time spent on fixation of highlighted object or area of interest  Best performance among 3 trials will be used.	Mixed ANOVA and post-hoc Bonferroni tests will be used to determine the differences between the Toric IOLs group and Monofocal IOLs group before surgery and 6 months after second eye surgery.
Refraction and visual acuity	-Visual acuity (vision, sphere, Cylinder, Axis, DVA, Add NVA) -IOL tilt and decentration -IOL rotation (for Toric IOL group only)	Interval  Average tilt, decentration and rotation of lens will be analysed by calculating average value in Toric and monofocal groups. Bland Altman will be used to study the agreement of position-level of error for IOLs tilt, decentration and rotation.	Mixed ANOVA and post-hoc Bonferroni tests will be used to determine the differences between the Toric IOLs group and Monofocal IOLs group before surgery and 6 months after second eye surgery.  Unaided and aided distance visual acuity will be recorded in Log MAR and comparisons between the two lenses pre and post cataract surgery will be conducted using a two-way ANOVA. Post-operative refractive astigmatism will be analysed using the Alpins method*. Correlation between SIA and TIA will be assessed, and dependent t-tests will be used to analyse the remaining metrics in the two groups
Questionnaire	Short Fall Efficacy Scale International	Ordinal (non-parametric)	Mixed ANOVA and post-hoc Bonferroni tests will be used to determine the differences between the Toric IOLs group

Vision and balance changes after bilateral implantation of Toric IOLs  
IRAS ID: 286913

	Fear of Falling Questionnaire CAT-PROM 5 Quality of life Questionnaire		and Monofocal IOLs group before surgery and 6 months after second eye surgery.
--	---	--	--

\*Post-operative refractive astigmatism will be analysed using the Alpíns method. Cylindrical power and axis will be converted to vectors (J0 and J45; Equations 1 & 2).

Equation 1: Calculation of J0	$J0 = J \cos 2\alpha$ 
J0 = cylindrical effect at 180° J = cylindrical power a = axis in radians

Equation 2: Calculation of J45	$J45 = J \sin 2\alpha$ 
J45 = cylindrical effect at 45° J = cylindrical power a = axis in radians

Target induced astigmatism (TIA) is the astigmatic correction predicted to occur and will be calculated with Equation 3.

Surgically induced astigmatism (SIA) is the astigmatic correction achieved post-operatively and calculated as Equation 4.

Equation 3: Target induced astigmatism	$TIA = \sqrt{((PreOp J0 - Predicted residual J0)^2 + (PreOp J45 - Predicted residual J45)^2)}$
Equation 4: Surgically induced astigmatism	$SIA = \sqrt{((PreOp J0 - PostOp J0)^2 + (PreOp J45 - PostOp J45)^2)}$

The Correction index (CI) is the ratio of SIA to TIA (Equation 5) and difference vector is the difference between TIA and SIA (Equation 6).

Equation 5: Correction Index	$CI = SIA/TIA$
Equation 6: Difference Vector	$Difference Vector = TIA - SIA$

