### **3.5 Secondary endpoints/outcomes**

1. The eye tracking characteristics (gaze duration, area of interest by gaze pattern and its percentage duration gaze time).

Vision and balance changes after bilateral implantation of Toric IOLs  
IRAS ID: 286913

2. IOL rotation by measuring degrees of rotation from intended position and degrees rotation from steepest meridian with digital slit lamp and IOL tilt and decentration using Pentacam4. This will be part of the routine eye assessment for post cataract surgery with Toric IOL.
3. Visual acuity which is also part of routine eye assessment for all post cataract surgery patients.
4. Fear of falling and fall efficacy scale via questionnaire.
5. Cataract specific quality of life questionnaire (CAT-PROM 5)

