Figure 1. Set up with movement sensor and eye tracking device (a) and movement sensors placement reinforced with tape (b)

Vision and balance changes after bilateral implantation of Toric IOLs  
IRAS ID: 286913

Figure 2. Example of eyetracking analysis using Tobii pro lab software: a) study of gaze on defined area of interest (stool in this example) and b) heat map analysis

[figure not shown]

Figure 3. Example of movement sensor output data using Promove 3D software

Vision and balance changes after bilateral implantation of Toric IOLs  
IRAS ID: 286913

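### For stair walking, the gaze area of interest is chosen from the same gaze data that are then scored, at an unstated level, and no test of gaze location is given

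*Combined protocol and SAP*

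**What the plan says.** The gaze row of section 10.3.3 lists two kinds of target: "Gazing duration on obstacles and area of interest on environment during stair walking". The obstacle is a physical object. For the other target the row gives a rule based on the recorded gaze: "Area of interest determined by heat map (area with highest frequency of gazing". The measure is the percentage of "time spent on fixation of highlighted object or area of interest". Section 3.5 names the endpoint in the same order: "area of interest by gaze pattern and its percentage duration gaze time". The outcome table in 10.3.1 gives the obstacles as the target for obstacle negotiation. For stair walking it gives only an area of interest and its gaze duration. No step edge, handrail, landing or other stair region is named anywhere.

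The row also says "Gaze pattern of location of hotspots and duration of gaze will be collected using Tobii pro eye tracker". The data type is interval, and the only analysis stated is mixed ANOVA with Bonferroni post-hoc tests. Of the three trials, "Best performance among 3 trials will be used"; what counts as best for gaze is not defined.

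Two other places bear on the point. The caption of Figure 2 in section 7.6 shows a "study of gaze on defined area of interest (stool in this example") as one analysis and a heat map as a separate one. Section 7.6 also says that the stair task uses a standardized staircase.

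**The concern.** An area picked because it drew the most gaze, and then scored for how much gaze it drew, yields a maximum. A maximum describes how concentrated gaze is; it does not say where gaze went. What follows depends on the level at which the heat map is built, which the plan leaves open:

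- **Per participant or per arm:** the scored area may be a different object in different people or arms. If one arm moves its gaze from one part of the stairs to another, both arms can score the same.
- **Per visit:** scores before and after surgery may refer to different places, so a change over time can vanish in the same way.
- **Pooled over everyone:** all scores refer to one place, but only that place is tested.

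Because the level is not fixed, the choice can also be made after the data are seen. At stake is the stair part of the secondary objective in section 3.2, which is to compare eye-tracking characteristics between the lenses. A real difference in where the two arms look could be recorded and yet have no stated test that would find it.

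**Working it through.** The documents give no planning figure for the gaze outcome. The sample size in 10.1 is for dynamic balance and is unaffected. It reproduces: with f = 0.25, alpha 0.05, two time points and an assumed within-person correlation of 0.5, the noncentrality is 0.25² × 110 × 2 / (1 + 0.5) = 9.17. Power at 110 participants is then 85.1%, against the planned 85%. Only the 55 per group is carried forward. All zones, gaze shares and fixation counts below are assumptions for illustration.

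**Step 1: two arms prefer different zones.** Take four stair zones. Arm A's gaze shares are 50/20/20/10% and arm B's are 20/50/20/10%.
- Fixed zone 1: 50% against 20%, a difference of 30 points.
- One hotspot per arm: zone 1 for A and zone 2 for B, so 50% against 50%, a difference of 0.
- One hotspot per participant, with n = 20 fixations: the expected score is E[max(X1,…,X4)]/n, where X is multinomial(n, p). This is 0.506 in each arm, because the two sets of shares are the same numbers reordered.

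I simulated 55 per arm with a two-sample t-test at 0.05, a simplification of the mixed ANOVA. Own-hotspot scoring rejects about 5 to 6% of the time, which is the nominal error rate. The fixed zone rejects 100%.

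**Step 2: the same question under another model.** Take five regions, with individual shares varying around the arm mean (Dirichlet, concentration 20), 55 per arm and 2000 runs. The full swap exchanges 40% and 25% between regions 1 and 2. The partial shift moves region 1 from 40% to 33%, with the difference going to region 2.

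| Scoring | Full swap: means | Full swap: rejection | Partial shift: rejection |
|---|---|---|---|
| Own hotspot | 0.423 v 0.422 | 5.4% | 32% |
| Fixed region 1 | 0.40 v 0.25 | 100% | 93% |
| One pooled hotspot | region varies by run | 100% | 93% |

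With no true difference, the pooled hotspot rejects 5.0%, so it does not inflate the type I error here.

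**Step 3: where a pooled hotspot fails.** Let arm A be 40/30/20/10% and arm B 40/10/40/10%. Averaged over arms, the zones are (40+40)/2 = 40, (30+10)/2 = 20, (20+40)/2 = 30 and (10+10)/2 = 10, so zone 1 is the pooled hotspot. Both arms score 40% on it, although they differ by 20 points on zone 2 (30 against 10) and by 20 on zone 3 (20 against 40). In the simulation with 20 fixations and 55 per arm, the pooled hotspot rejects 5% and fixed zone 2 rejects 100%.

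**Step 4: does the number of recorded fixations matter?** The expected own-hotspot share for 10, 20 and 40 fixations is:
- shares 50/20/20/10%: 52.6%, 50.6% and 50.1%, a movement of 2.5 points;
- no preference (25% each): 42.0%, 36.9% and 33.3%, a movement of about 9 points.

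The larger movement needs participants with no preferred place to look.

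**The case against.** The strongest reply is that the plan never says the heat map is per participant. That is correct. A reader might infer that the area is wherever each participant looked most, and conclude that the endpoint is circular as a matter of fact. The text does not support that: the level is unstated, and one pooled hotspot recovers the shifts in steps 1 and 2 in full. What remains is that the plan leaves the choice open, and that the pooled version has the gap shown in step 3.

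The obstacle measure also stands. Its target is a fixed object, so it would be wrong to call the whole gaze outcome circular.

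Nor is location lost, since hotspot location and heat maps are recorded. It is too strong to say that the trial could not see a shift. The supported statement is that the row's only test, a mixed ANOVA on interval data, does not compare locations.

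It is also tempting to say that recording length alone moves the endpoint by 9 points. Step 4 shows that this holds only without any gaze preference; under 50/20/20/10% shares the movement is about 2.5 points. The documents give no reason to expect recording length to differ between arms.

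Finally, concentration of gaze is a legitimate eye-tracking characteristic, and the objective does not say that location is the question. If concentration is what is wanted, the plan should say so. As written, the endpoint reads as time on an area, and readers would take it as evidence about that area.

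**Conclusion.** The point holds for stair walking, in conditional form. The area of interest is taken from the data that are then scored, the level of the heat map is not stated, and hotspot location has no stated test. With a hotspot per participant or per arm, a 30-point difference on a fixed zone can shrink to about zero (about 51% against 51%), and rejection stays near the nominal 5%. With one pooled hotspot, a 20-point shift between other zones can go untested. These sizes rest on assumed zones, shares and fixation counts. They show what the rule permits and do not forecast this trial.

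The importance is moderate. Sections 3.5 and 10.3.3 treat gaze as secondary, and the sample size does not depend on it. The table in 10.3.1 lists gaze under primary outcomes; that conflict should be reconciled, because a primary role would raise the stakes.

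**What to change.** In 10.3.3 and 3.5, replace the heat-map rule for stair walking with a list of areas of interest fixed before any data are viewed, for example leading step edges, handrail, landing and floor ahead. Use the same set for every participant, visit and arm, with gaze mapped to areas by staff masked to arm. Make the outcome the percentage of valid gaze time on each named area, and keep heat maps as descriptive figures. In the same edit, state what best performance means for gaze.

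The cost is protocol and SAP wording plus one area-of-interest template. The standardized staircase allows a single template, and Figure 2 shows that the planned software already handles a defined area. The downside is that a hotspot nobody foresaw would be described but not tested.

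### Refractive axis in degrees falls under the mean ± SD and mixed ANOVA with no exemption, and the J0/J45 components that would handle it are not compared between arms

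*Combined protocol and SAP*

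**What the plan says.** Four statements bear on axis.

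- **Data collected (section 10.3.3, refraction row).** The list is "Visual acuity (vision, sphere, Cylinder, Axis, DVA, Add NVA", and the data-type cell for the row reads interval. The table in section 10.3.1 also has axis among the recorded outcomes.
- **Test (same row).** "Mixed ANOVA and post-hoc Bonferroni tests will be used to determine the differences between the Toric IOLs group and Monofocal IOLs group before surgery"; the row's other time point is the one that follows the second operation. Section 10.3 extends the mixed ANOVA to baseline characteristics.
- **Summary (section 10.3).** "Descriptive summary statistics for outcome measures relating to vision (acuity and refraction) will be recorded as mean +/- standard deviation".
- **Astigmatism method (same row and its footnote).** "Post-operative refractive astigmatism will be analysed using the Alpins method", and "Cylindrical power and axis will be converted to vectors (J0 and J45" by the double-angle formulas in Equations 1 and 2. Equations 3 and 4 form target and surgically induced astigmatism (TIA and SIA). For the rest: "The Correction index (CI) is the ratio of SIA to TIA (Equation 5) and difference vector is the difference between TIA and SIA (Equation 6".

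No sentence keeps axis in degrees out of the summary or the ANOVA, and none says that J0 and J45 take its place there.

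**The concern.** Axis is circular: 5 and 175 degrees are 10 degrees apart, but their arithmetic mean is 90. An analyst who follows the general wording would average and test axis in degrees, and near the wrap the result can be wrong in size and in sign.

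Astigmatism is what the two lenses treat differently, so its direction before and after surgery is part of the explanatory evidence. Section 1 says that most astigmatism has its steep curve vertical and that some has it horizontal. Whichever cylinder sign convention is used, one of these two orientations has its axis at 0/180. The documents do not state the convention, so the share of eyes near the wrap is unknown.

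**Working it through.** The plan gives no figure for axis, so there is none to reproduce. The inputs are Equations 1 to 6 (section 10.3.3 footnote) and 55 per group (section 10.1). **Assumed**, because the documents do not give them: normally distributed axes with SD 10 degrees, the centres shown below, and a cylinder of 2 D.

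**1. Two eyes, axes 5 and 175 degrees.**
- In degrees: mean (5 + 175)/2 = 90; SD = 170/√2 = 120.
- By Equations 1 and 2: J0 = 2 cos 10° = 1.97 and 2 cos 350° = 1.97; J45 = 2 sin 10° = +0.35 and 2 sin 350° = −0.35. The mean vector is (1.97, 0), which is axis 0 (= 180). That is correct.

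**2. One arm centred on the wrap, N(180, 10) reduced to 0–180.**
- Half the values fall just above 0 and half just below 180. The mean distance from the wrap is 10√(2/π) = 7.98, so the halves have means 7.98 and 172.02.
- Overall mean = 90.
- Within each half the SD is 10√(1 − 2/π) = 6.03. Overall SD = √(82.02² + 6.03²) = 82, against a true 10.

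**3. Two arms centred at 175 and 5 (= 185).**
- Share that wraps in each arm: P(Z > 0.5) = 0.3085, and 180 × 0.3085 = 55.5.
- Arithmetic means: 175 − 55.5 = 119.5 and 5 + 55.5 = 60.5.
- Apparent difference: 60.5 − 119.5 = −59 degrees. The true difference is +10.

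**4. Simulation.** 55 per arm, 4,000 runs, SD 10. A two-sample t-test stands in for the between-arm comparison at one visit.

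| Arm centres | True difference | Mean difference in degrees | Significant, raw axis | Significant, sin 2a |
|---|---|---|---|---|
| 180 and 180 | 0 | −0.4 | 5.4% | 4.6% |
| 178 and 182 | +4 | −24.7 | 35% | 55% |
| 175 and 185 | +10 | −59.1 (wrong sign) | 97% | over 99% |
| 88 and 92 | +4 | +4.0 | 56% | 56% |

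With identical arms, the test keeps its error rate. Away from the wrap, raw axis and the double-angle component agree. The damage occurs when the values straddle 0/180, and it shows as a false direction when the arms differ.

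**5. Do Equations 3 to 6 supply a directional comparison?** Equations 3 and 4 are square roots of summed squares, so TIA and SIA are lengths. Equation 5 is their ratio and Equation 6 subtracts one length from the other. With both at 2 D and a 10-degree axis error, Equation 6 gives 2 − 2 = 0 D, while the vector difference has length 2 × 2 × sin 10° = 0.69 D. Direction enters through J0 and J45 and is not returned by any later quantity.

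**The case against.** The strongest reply is that the row already contains the right method. The mixed-ANOVA sentence is a general one, repeated almost unchanged down the outcome tables. Here it is followed by specific methods: LogMAR with a two-way ANOVA for acuity, and the Alpins analysis for astigmatism, with "Cylindrical power and axis will be converted to vectors (J0 and J45; Equations 1 & 2". On the natural reading the specific text governs axis. Axis is also only a recorded component of refraction: the endpoint lists in sections 3.5 and 3.6 name visual acuity and IOL rotation, not refractive axis.

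Much of this stands. A reader might infer that the plan has no method for the wrap, and that is not so: the conversion is correct and is in the same row. It does not close the gap, for three reasons.

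- The Alpins sentence covers post-operative astigmatism. It does not withdraw axis from the mean ± SD or from the baseline comparison.
- J0 and J45 feed only the quantities in step 5. The remaining metrics are assigned dependent t-tests without being listed. J0 and J45 are neither named nor excluded, and a dependent t-test is a paired test, not a comparison of independent arms.
- IOL rotation cannot stand in for direction, because section 10.3.3 restricts it to the Toric group.

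It is also fair to object that a single cluster at the wrap is a worst case, since section 1 describes horizontal and oblique astigmatism too.

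**Conclusion.** The point holds as a minor gap in a secondary analysis. Read as written, the plan summarises and tests axis in degrees, and it specifies no valid directional comparison between arms. The sizes above (SD 82 for a true 10; −59 degrees for a true +10) are illustrations. They rest on the assumed distributions and apply only to values that straddle 0/180.

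Two stronger readings are not supported. One is that the refraction analyses as a whole would be meaningless: sphere, acuity and cylinder power are not affected by the wrap. The other is that the wrap would create arm differences where none exist: with identical distributions the false-positive rate stays near 5%. What the wrap does is distort the size and sign of a real difference, and distort the summaries even when there is no difference.

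The primary outcome is dynamic stability and the sample size was calculated for it, so neither is affected.

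**What to change.** Amend sections 10.3 and 10.3.3 to state that:

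- axis in degrees is recorded but is left out of the mean ± SD summaries and the mixed ANOVA, at baseline and after surgery;
- J0 and J45 from Equations 1 and 2 are summarised and compared between arms in its place, alongside cylinder magnitude.

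The cost is a few sentences in the analysis plan. J0 and J45 are already to be computed, and no new data, visits or participants are needed. Confidence ellipses around the arm means and double-angle plots would present the result well, but they are optional.
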